## 2.6 Correlative Studies

To determine the role of residual AML stem cells on efficacy of lenalidomide maintenance after autotransplant.

Myeloid malignancies can arise from a small population of quiescent cancer-initiating cells that are not eliminated by conventional cytotoxic therapies. Eliminating leukemia stem cells can reduce the rates of relapse and increase leukemia free survival. Thus it is important to evaluate the role of persistent leukemia stem cells in the efficacy of lenalidomide maintenance regimens.

Flow cytometry will be done on bone marrow aspirates to estimate the persistence of leukemic stem cells. We have established protocols to isolate rigorously defined long-term hematopoietic stem cells (LT-HSC, Lin, CD34+, CD38, CD90+), short-term hematopoietic stem cells (ST-HSC, Lin, CD34+, CD38, CD90^-), common myeloid progenitors (CMP, Lin, CD34+, CD38+, CD123+, CD45RA), granulocyte-monocyte progenitors (GMP, Lin, CD34+, CD38+, CD123+, CD45RA+), and megakaryocyte-erythrocyte progenitors (MEP, Lin, CD34+, CD38+, CD123, CD45RA) from primary bone marrow aspirates. Sorted cells will have FISH studies done on them to estimate the number of stem cells with clonal cytogenetic alterations (Leukemic stem cells). Functional assays will also be done on these sorted cells to demonstrate clonogenic potential in vitro, and leukemia-initiating potential in vivo. A recently discovered marker of AML stem cells, IL1RAP, will also be evaluated on AML stem cells and correlated with clinical response.

Whole transcriptome sequencing, exome sequencing, and global methylome analysis on sorted cells will also be done and correlated with response. This will allow us to correlate molecular markers with relapse or remission.

Detailed procedures for correlative studies are discussed in Section 7.

### **3. PATIENT SELECTION**

#### **3.1 Inclusion Criteria**

- 3.1.1. Patients must have a Confirmed diagnosis of non-M3 AML. Antecedent MDS is acceptable.
- 3.1.2. Post autologous Stem Cell Transplant Bone marrow biopsy core that is consistent with morphologic remission.
- 3.1.3. Age between 60 and 80years old.
- 3.1.4. Must have received induction and consolidation chemotherapy, and autologous stem cell transplant for AML.
- 3.1.5. Life expectancy of greater than 12 months.
- 3.1.6. Karnofsky Performance Status 70 or greater (see Appendix A)
- 3.1.7. Patients must have normal organ and marrow function as defined below:
  - Leukocytes  $\geq 2,000/\text{mCL}$
  - Absolute neutrophil count  $\geq 1,000/\text{mCL}$
  - Platelets  $\geq 75,000/\text{mCL}$
  - Total bilirubin  $\leq 4 \times$  institutional upper limit of normal unless 2nd to Gilbert's disease
  - AST(SGOT) and ALT(SGPT)  $\leq 4 \times$  institutional upper limit of normal
  - Creatinine  $< 1.5 \times$  institutional upper limit of normal OR creatinine clearance  $\geq 30 \text{ mL}/\text{min}/1.73 \text{ m}^2$  for patients with creatinine levels above institutional normal.
- 3.1.8 Able to take aspirin, or warfarin, or low molecular weight heparin as prophylactic anticoagulation.
- 3.1.9. Ability to understand and the willingness to sign a written informed consent document.
- 3.1.10 Must be registered into the mandatory RevAssist® program and be willing and able to comply with the requirement of RevAssist®.

#### **3.2 Exclusion Criteria**

- 3.2.1. Patient received chemotherapy or radiotherapy within 2 weeks prior to entering the study or has not recovered from adverse events due to agents administered more than 4 weeks earlier.
- 3.2.2 Patient received another investigational agent after post autologous stem cell transplant.
- 3.2.3 Patient who will be receiving another investigational product during the study.

- 3.2.4 Patient who is growth factor or transfusion dependent.
- 3.2.5 Patient has CNS leukemia.
- 3.2.6 History of allergic reactions attributed to thalidomide or lenalidomide.
- 3.2.7 History of erythema nodosum, characterized by a desquamating rash while taking thalidomide or similar drugs.
- 3.2.8 Prior history of metastatic malignancy.
- 3.2.9 Uncontrolled illness including, but not limited to ongoing or active infection, unstable angina pectoris, cardiac arrhythmia, or psychiatric illness/social situations that would limit compliance with study requirements. Patients must not have suffered recent (< 6 months) myocardial infarction, unstable angina, uncontrolled hypertension, or difficult to control cardiac arrhythmias.
- 3.2.10 Evidence of uncontrolled Congestive Heart Failure (CHF).
- 3.2.11 Active Hepatitis B as defined by Hepatitis B surface antigen positivity, unless able to start dual anti-HepB therapy, or already on dual anti-HepB therapy
- 3.2.12 Patients who are positive for Hepatitis B core antibody, but negative for the hepatitis B surface antigen, should be on lamivudine 100 mg daily until at least 3 months post-transplant
- 3.2.13 Patient is positive for HIV or HTLV-1.
- 3.2.14 Women of childbearing potential (defined as a sexually mature woman who has not undergone a hysterectomy or who has had menses at any time in the preceding 24 consecutive months).
- 3.2.15 Men who did not agree not to father a child and who refused to use a latex condom during any sexual contact with women of childbearing potential while taking lenalidomide and for 4 weeks after therapy is stopped, even if they have undergone a successful vasectomy.

### 3.3 Inclusion of Women and Minorities

Both men and women and members of all races and ethnic groups are eligible for this trial.

## 4. REGISTRATION PROCEDURES

### 4.1 General Guidelines

The coordinating center is: **Montefiore-Einstein Cancer Center**  
**Montefiore Medical Center-Moses Division**  
Department of Oncology, [name]  
[name]  
[name]  
[contact] or [contact]  
[contact] or [contact]

Coordinator: [name]  
Email: [[contact]](mailto:[contact])

Eligible patients will be entered on study centrally at the Montefiore-Einstein Cancer Center Coordinating Center by the Study Coordinator. All sites should call the Study Coordinator [name]; [contact] to verify eligibility. The required forms (eligibility and registration form; form 1) can be found in the Appendix (Appendix B).

Following registration, patients should begin protocol treatment within 96 hours. Issues that would cause treatment delays should be discussed with the Principal Investigator (PI). If a patient does not receive protocol therapy following registration, the patient's registration on the study may be canceled. The Study Coordinator should be notified of cancellations as soon as possible.

#### 4.2 Registration Process

To register a patient, the following documents should be completed by the research nurse or data manager and faxed or e-mailed to the Study Coordinator at the Montefiore-Einstein Cancer Center Coordinating Center [name]; [contact], [contact] or email: [[contact]](mailto:[contact])

- Form 1 (Appendix B)
- Copy of required laboratory tests and procedures
- Signed patient consent form
- HIPAA authorization form

The research nurse or data manager at the participating site will then call the Study Coordinator at the Montefiore-Einstein Cancer Center Coordinating Center [name], [contact], [contact] or email: [[contact]](mailto:[contact]) to verify eligibility. To complete the registration process, the Coordinator will - after discussion with the PI, [name]:

[figure not shown]
- Assign a patient study number
- Register the patient on the study
- Fax or e-mail the patient study number to the participating site
- Call the research nurse or data manager at the participating site and verbally confirm registration.

Once patients are found eligible for the study, they will be registered with the Montefiore-Einstein Cancer Center Coordinating Center. A patient number will be assigned, and a copy of appendix B including the patient number will be faxed back to the participating center/investigator.

## 5. TREATMENT PLAN

Treatment will be administered on an outpatient basis. Lenalidomide 2.5 mg, 5 mg, 10 mg, 15 mg and 25 mg capsules are to be taken orally (PO). In Phase I, the starting dose of Lenalidomide is 10 mg taken PO daily for 3 consecutive weeks (Days 1-21) following one week off therapy (Days 22-28). One cycle is 4 weeks (Figure 1).

**Figure 1:** Phase 1 and Phase 2 Lenalidomide Dosing Schema

In phase 1, it is anticipated that 6 - 18 evaluable patients will be treated. Three to six patients will be treated at each dose level of three dose levels of Lenalidomide (10 mg, 15 mg, 25 mg) daily doses (Table 1). The initial dose is 10 mg. Patients will receive repeated cycles of Lenalidomide until disease progression or unacceptable toxicity. If no Lenalidomide related Dose Limited Toxicity (DLT) is seen in three patients at a dose level during first cycle (by day 28), the escalation to the next dose level is allowed. Each cohort will be monitored for a DLT during the first cycle before deciding to escalate the dose for the next cohort.

**Table 1:** Phase 1 Dose ranging

Dose Level	Daily Dose (once a day)	Number of Patients	Escalation Rule *
-1	5 mg	3 – 6	If 0/3 DLT or 1/3 DLT add 3 patients
1 (Starting Dose)	10 mg	3 – 6	If 0/3 DLT escalate 1/3 DLT add 3 patients
2	15 mg	3 – 6	If 0/3 DLT escalate 1/3 DLT add 3 patients
3	25 mg	3 – 6	If 0/3 DLT or 1/3 DLT add 3 patients

\* Dose escalation rules are described in details in Table 2.

Dose escalation determination is summarized in Table 2. If one DLT occurs at a dose level, up to 3 additional patients will be added to that cohort and if one or more of this group suffers DLT, then dose escalation is stopped, and this dose is declared the Maximally Tolerated Dose (MTD). Three additional patients will be entered at the next lower dose level if only three patients were treated previously at that dose.

**Table 2:** Determination of Lenalidomide Capsules Maximum Tolerated Dose (MTD)

Number of Patients with DLT at Given Dose Level	Dose Escalation Rule
0 out of 3	Enter three patients at the next dose level
≥ 2	Dose escalation will be stopped. This dose level will be declared MTD. Three additional patients will be recruited at the next lower dose level if only three patients were treated previously at that dose.
1 out of 3	Recruit at least three more patients at this dose level. 
 
• If none of these patients experience with DLT, proceed to the next higher dose level
 
• If one or more of this group suffer DLT, then dose escalation is stopped and this dose is declared MTD. Three additional patients will be entered at the next lower dose level if only three patients were treated previously at that dose.
 

≤ 1 out of 6 at highest dose level below the MTD	This will be the recommended Phase 2 dose. At least six patients must be recruited at the recommended Phase 2 dose.

If no DLT is observed at the final 25 mg dose level in the first three patients, three additional patients at the 25 mg dose level will be recruited. In Phase 1, in order to declare Therapeutic Dose Level (TDL), a minimum of six patients must be recruited at that dose level. Therapeutic

Dose Level (TDL) is defined as the dose level where DLT occurred in less or equal to one out of six patients below the Maximally Tolerated Dose level. TDL will be the recommended dose for Phase 2.

If a DLT is observed in two or more patients at the first dose level (10 mg), then dose level -1 (5 mg) will be tested with three patients first. Three additional patients will be enrolled at the 5 mg dose, if one or less DLT is observed. If one or more of this group suffers DLT, then the study is stopped and lenalidomide maintenance for elderly AML patients post autologous transplant is not deemed feasible (same as if  $\geq 2$  had a DLT to initial cohort of 5 mg).

Decisions about DLTs, expansion of a cohort to six subjects, escalation to the next dose level, or reduction to the next lower level will be made by Principle Investigator.

In Phase 1, subjects will continue study drug, lenalidomide until disease progression or unacceptable toxicity. Reported adverse events and potential risks for lenalidomide are described in Section 2.5. Dose modifications are described in Sections 5.1 and in Table 3. Subjects who are withdrawn without a DLT before completing Cycle 1 will not be used to evaluate the MTD or TDL, but will be included in the overall safety analysis.

In Phase 2, patients will receive the lenalidomide dose recommended in the Phase 1 portion. 30 patients will be enrolled in Phase 2. Study procedures are the same as the Phase 1 portion. Subjects will be able to continue the study treatment until disease progression or unacceptable toxicity. Detailed discontinuation information is provided in Section 5.4.

A new course of treatment may begin on the scheduled day 1 of a new cycle if;

- Absolute neutrophil count  $\geq 1,000$  / mL
- Platelets count  $\geq 50,000$
- Resolution of adverse events to  $\leq$  grade 1 (Details in Section 5.1).

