### **5.1 Dose modifications**

At Phase 1, subjects who develop any DLT during cycle 1 will be taken off the study. During cycle 2 and onward, dose reductions are allowed. Dose reduction rules are the same for subjects enrolled in Phase 2 (Table 3). Reduced doses will not be re-escalated for any subject during the study. Subjects may not continue Lenalidomide after the third dose reduction or beyond dose of 2.5 mg.

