**Table 3: Lenalidomide Capsules Dose Modifications**

Original Daily Dose (mg)	First Dose Reduction (mg)	Second Dose Reduction* (mg)	Third Dose Reduction* (mg)
5	2.5	Discontinue	N/A
10	5	2.5	Discontinue
15	10	5	2.5
25	15	10	5

\* Subjects may not continue Lenalidomide after third dose reduction or beyond dose of 2.5 mg.

A non-hematologic DLT is defined as a National Cancer Institute (NCI)-Common Terminology Criteria for Adverse Events (CTCAE) Version 4 (Oct/09) Grade 3 or 4 adverse events (AE) considered related to the study drug. Grade 3 anorexia and Grade 3 fatigue are excluded since it is very common to develop anorexia and fatigue during any chemotherapy.

A hematologic DLT is defined as a grade 4 hematologic toxicity complicated by infection, severe hemorrhage, or marrow aplasia persisting greater than 2 weeks considered related to the study drug.

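### The aplasia DLT needs more than two weeks but the cohort is read at day 28, so aplasia starting on days 15-28 cannot count at the escalation decision and the plan does not clearly say how to treat it afterwards

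*Combined protocol and SAP*

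**What the plan says.** - **Escalation (Section 5).** If no lenalidomide-related DLT is "seen in three patients at a dose level during first cycle (by day 28), the escalation to the next dose level is allowed". A further sentence says that each cohort is watched for DLT in the first cycle before the next dose is decided. Cycle 1 is 28 days, with drug on days 1-21.
- **DLT definition (Section 5.1, below Table 3).** A hematologic DLT is a grade 4 toxicity complicated by infection, by severe hemorrhage, or by "marrow aplasia persisting greater than 2 weeks considered related to the study drug". No onset or completion window is given.
- **Table 2.** For 0 of 3: "Enter three patients at the next dose level". For 1 of 3: "Recruit at least three more patients at this dose level".
- **TDL (Section 5).** It is "defined as the dose level where DLT occurred in less or equal to one out of six patients below the Maximally Tolerated Dose level". This sentence carries no time window.
- **Evaluability (Section 5).** "Subjects who are withdrawn without a DLT before completing Cycle 1 will not be used to evaluate the MTD or TDL". A patient who completes cycle 1 with a toxicity still running is not mentioned.
- **Patient management.** Under Section 5.1, "subjects who develop any DLT during cycle 1 will be taken off the study". Section 5.1.1, which for Phase 1 applies after cycle 1, lets the drug be held for up to 8 weeks and restarted one level lower.
- **Next cycle (Section 5).** "A new course of treatment may begin on the scheduled day 1 of a new cycle if" the neutrophil count is at least 1,000, platelets are at least 50,000, and adverse events have resolved to grade 1 or less.
- **Who decides (Section 5).** The Principal Investigator rules on DLTs, cohort expansion and escalation.

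**The concern.** A criterion that takes more than 14 days to meet is read at a fixed day 28. Half of the possible onset days therefore lie too late for it. The other two hematologic criteria, infection and severe hemorrhage, have no duration and are not affected. Aplasia, however, is the only one that catches severe cytopenia without such a complication, and Table 5 in Section 9.8 itself expects myelosuppression from this drug.

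Two things are at stake. Followed literally, the plan may expose three new patients to a higher dose while a grade 4 aplasia in the current cohort is still open. And once that aplasia passes two weeks, the texts do not settle how to tally it or how to manage the patient.

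**Working it through.** **Plan's own figures.** The plan states no figure on this point. The Phase 1 size that frames it, 6-18 evaluable patients, reproduces: 3 levels x 6 = 18 at most, and 3 at 10 mg plus 3 at 5 mg = 6 at least. It is not in dispute.

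**1. Which onset days can count by day 28.** Onset on day d reaches more than 14 days by day 28 if 28 - d + 1 > 14 (days counted inclusively) or 28 - d > 14 (elapsed days).
- Inclusive: d ≤ 14. Elapsed: d ≤ 13.
- Onset on day 15 first qualifies on day 29 or 30; on day 21, on day 35 or 36; on day 28, on day 42 or 43.

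Under either count, onset on days 15-28 (14 of 28 days) cannot qualify by day 28.

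**2. One patient through the rules.** Take aplasia from day 20, still present at day 28, in a cohort with no other DLT.

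| Question | If the day-28 reading is final | If the event counts once it passes two weeks |
|---|---|---|
| Cohort tally | 0/3: next dose level | 1/3: three more at this level |
| MTD/TDL count | not counted | counted |
| Patient | held, restarted one level lower (5.1.1) | off study (5.1) |

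The start-of-cycle criteria stop this patient's own cycle 2. They do not hold the next cohort.

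**3. How many patients are open at the decision.** At 8 patients a year (Section 10.2) the mean interval is 365.25/8 = 45.7 days. When the last patient of a group reaches day 28, the one before is near day 28 + 45.7 = 74, so any cycle 1 aplasia in that patient is already classified. Usually only the last patient is open.

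**4. Illustrative size.** The documents give no rates. Assume a chance q of prolonged aplasia with cycle 1 onset, no other DLTs, and a share of late onsets (after day 14) of 14/28 = 0.50 (onset uniform over days 1-28) or 14/21 = 0.67 (uniform over days 8-28). A level passes as 0/3, or as 1/3 followed by 0/3.
- Counted by onset: P = (1-q)³ + 3q(1-q)² × (1-q)³.
- Strict day-28 reading, last patient of each group open, r = q(1 - late share): A = (1-q)²(1-r); B = 2q(1-q)(1-r) + (1-q)²r; P = A + B × A.

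Example, q = 0.10 and late share 0.50: r = 0.05, A = 0.7695, B = 0.2115, P = 0.932, against 0.906 by onset.

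| q | By onset | Strict day 28 | Gap |
|---|---|---|---|
| 2% | 0.995 | 0.997 | 0.001-0.002 |
| 5% | 0.973 | 0.981-0.984 | 0.008-0.010 |
| 10% | 0.906 | 0.932-0.940 | 0.026-0.034 |
| 20% | 0.709 | 0.779-0.801 | 0.070-0.093 |

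The strict column assumes that the late event is never counted and that nobody waits, so for this accrual pattern it is an upper figure.

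**The case against.** The strongest reply is that the texts, read literally, give one answer. The window is cycle 1, to day 28. A criterion first met on day 30 was not met in cycle 1, so the patient is not removed under Section 5.1 and falls under the hold-and-reduce rule of 5.1.1. That reading is coherent, but the plan does not state it: the DLT definition, Table 2 and the TDL sentence carry no window. It is also the reading under which Table 2 opens the next dose with a grade 4 toxicity unresolved.

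The second reply is that the event will be noticed and the Principal Investigator can wait, since escalation is only allowed. This largely stands. Related adverse events are followed to resolution (Section 9.1), Table 5 makes neutropenia or thrombocytopenia lasting more than 15 days reportable, and Section 11.1 provides frequent Principal Investigator review, biweekly calls and monthly committee review. These make detection likely. They do not say how the event is tallied or that the cohort is held.

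Three stronger readings are tempting, and the documents do not support them.
- A reader might infer from the visit schedule that late aplasia could not be confirmed until the Cycle 2 Week 3 visit, nominally day 43. That assumes cycle 2 starts on time. The start-of-cycle criteria block this patient, and showing recovery needs repeat counts.
- A reader might infer that sites would tally the same event differently. One Principal Investigator makes all DLT decisions and registration is central.
- A reader might apply the day-28 miss to every patient in a group. That would give gaps of about 0.07-0.08 at q = 10% and 0.20-0.25 at 20%, but at the planned accrual the earlier patients are already classified.

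**Conclusion.** The point holds as a gap in the escalation rule, and it is modest. That onset on days 15-28 cannot qualify by day 28 follows from the text under either way of counting days. Two consequences also follow from the text: a literal reading enters patients at the next dose while the aplasia is open, and the later MTD/TDL tally and the patient's management are not clearly settled.

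The size rests on assumptions: the rate of prolonged aplasia, the onset pattern, no other DLTs, and only the last patient of a group open. With 10-20% prolonged aplasia, the chance that a level passes rises by about 0.03-0.09. At 2-5% the rise is 0.01 or less. It disappears if the Principal Investigator waits. A reader might infer that the plan will escalate past an unsafe dose; the documents give no rate that would support this, and they leave room to wait. The change is worth making because it is cheap and concerns exposure to a higher dose.

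**What to change.** Add to Section 5:

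> MTD and TDL counts use DLTs with onset in cycle 1 (days 1-28). If a grade 4 cytopenia is unresolved at day 28, counts are repeated at least weekly until it resolves or has lasted more than 14 days from onset; the patient is tallied, and the cohort decision made, only then.

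Add to Section 5.1:

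> Aplasia with onset in cycle 1 that lasts more than 14 days from onset is a cycle 1 DLT even if the 14 days are passed after day 28. Cytopenia with onset in cycle 1 that does not become a DLT is managed under 5.1.1.

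The last sentence is needed so that a shorter cytopenia starting late in cycle 1 (for example days 22-32) keeps the hold-and-reduce rule. State also that aplasia for this purpose is judged on blood counts, since no on-treatment marrow is scheduled until about Cycle 4 Week 1 (Section 6.2).

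**Cost.** One or two extra blood counts in affected patients, and a wait of at most about 15 days past day 28 (onset on day 28 is settled by day 42 or 43), only in cohorts with an open cytopenia. If arrivals are random, a new candidate appears during a 15-day wait with probability 1 - exp(-15/45.7) = 0.28. The wait is 15/85 = 18% of the screening window (post-transplant days 15-100, Section 6.1), so most candidates can wait, but one near day 100 may be lost. A patient with late aplasia who might have continued at a reduced dose is removed instead.

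### Section 5 and Table 2 give the name MTD to the dose that fails, and give opposite decisions (stop, or go to Phase 2) for 0/3 then 1/3 DLTs at 5 mg

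*Combined protocol and SAP*

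**What the plan says.** **The label.** Table 2, in its row for two or more DLTs, stops escalation and adds: "This dose level will be declared MTD". The row for 1/3 followed by a further DLT among the added patients does the same: "then dose escalation is stopped and this dose is declared MTD". The Section 5 text before Table 2 agrees with both rows. Secondary objective 1.2.1 is to define the MTD and to establish the TDL.

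**The Phase 2 dose.** Table 2 recommends for Phase 2 the level with at most 1 "out of 6 at highest dose level below the MTD". The TDL definition in Section 5 uses the same criterion, requires at least six patients, and makes the TDL the Phase 2 dose.

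**The 5 mg fallback.** This level opens after two or more DLTs at 10 mg. Table 1 says for it: "If 0/3 DLT or 1/3 DLT add 3 patients", and its footnote sends the reader to Table 2 for the detailed rules. The Section 5 text says: "Three additional patients will be enrolled at the 5 mg dose, if one or less DLT is observed". It continues: "If one or more of this group suffers DLT, then the study is stopped", with the conclusion that "lenalidomide maintenance for elderly AML patients post autologous transplant is not deemed feasible".

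**The concern.** There are two problems and one small gap.

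1. The dose named maximum tolerated is always one the plan has just rejected. Anyone who reads the objective 1.2.1 result at face value would take a dose at least one level too high as tolerable.
2. When 5 mg is opened because 10 mg failed, 10 mg carries the MTD label and 5 mg is the highest level below it. A total of 1/6 at 5 mg then meets the Table 2 and TDL criterion. The 5 mg paragraph stops the study for that same total if the DLT falls in the second three. What is at stake is whether Phase 2 takes place.
3. Minor: the TDL is defined only below the MTD, so a cleared 25 mg is not covered by the definition. The expansion to six at 25 mg, the six-patient minimum and the synopsis maximum make the intention clear, and no wrong dose follows.

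**Working it through.** **The plan's own figure.** Section 5 anticipates 6 to 18 evaluable Phase 1 patients. Following Tables 1 and 2 with one step down gives totals of 6, 9, 12, 15 or 18, which agrees. If the step-down rule is applied repeatedly from 25 mg to 5 mg, the total can reach 4 × 6 = 24.

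**Assumptions.** The documents give no DLT rates, so a range is used, listed in the order 5/10/15/25 mg. A level filled to six on de-escalation that then has two or more DLTs de-escalates again. 25 mg is filled to six unless two or more of the first three have a DLT.

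**Step 1: how often the label lands on a failed dose.** With DLT risk p and q = 1 − p:

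- pass at 10 or 15 mg = q³ + 3pq² × q³
- pass at 25 mg = P(at most 1 of 6) = q⁶ + 6pq⁵
- P(label on a failed dose) = 1 − product of the three passes

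At a flat 10%: 0.729 + 0.243 × 0.729 = 0.9061 at 10 and 15 mg; 0.5314 + 0.3543 = 0.8857 at 25 mg; 1 − 0.9061² × 0.8857 = 27.3%.

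The labelled dose has an observed rate from 2/6 (33%, exact 95% CI 4% to 78%) to 3/3 (100%).

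**Step 2: every outcome at 5 mg.**

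| First 3 | Added 3 | Total | Section 5 text (added three) | Section 5 text (all six) | Table 2 and TDL |
|---|---|---|---|---|---|
| 0 | 0 | 0/6 | Phase 2 | Phase 2 | Phase 2 |
| 0 | 1 | 1/6 | **stop** | **stop** | **Phase 2** |
| 1 | 0 | 1/6 | Phase 2 | **stop** | **Phase 2** |
| 0 | 2 or 3 | 2/6 or 3/6 | stop | stop | fails |
| 1 | 1 to 3 | 2/6 to 4/6 | stop | stop | fails |
| 2 or 3 | none | 2/3 or 3/3 | stop | stop | fails |

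If the stopping sentence refers to the added three, one outcome is in conflict, and the same 1/6 stops or continues by order alone. If it refers to all six, both orders conflict with Table 2. On de-escalation to 10 or 15 mg, 0/3 then 1/3 is accepted as the TDL.

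The wording looks like a drafting slip. For the escalation levels, the rule on one or more DLTs among the added patients applies only after one DLT has occurred, so it means two or more in total. At 5 mg the rule is reused although expansion also follows 0/3.

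**Step 3: how often the 5 mg conflict arises.** Given that 5 mg is opened, P(0/3 then 1/3) = q³ × 3pq² = 3pq⁵:

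- p = 5%: 0.15 × 0.7738 = 11.6%
- p = 10%: 0.30 × 0.5905 = 17.7%
- p = 20%: 0.60 × 0.3277 = 19.7%

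The whole-trial figure multiplies this by the chance that 5 mg is opened, taken from exact enumeration of the full scheme.

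| Assumed DLT rates | Label on a failed dose | 5 mg opened | 0/3 then 1/3 at 5 mg, whole trial |
|---|---|---|---|
| 5/5/5/5% | 8.35% | 2.67% | 0.31% |
| 10/10/10/10% | 27.27% | 9.58% | 1.70% |
| 20/20/20/20% | 67.09% | 30.79% | 6.05% |
| 5/10/20/30% | 73.02% | 10.04% | 1.17% |
| 10/20/30/40% | 91.83% | 32.13% | 5.69% |
| 20/30/40/50% | 98.33% | 56.19% | 11.05% |

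The last column doubles on the all-six reading, because 1/3 then 0/3 has the same probability. A simulation of 200,000 trials at a flat 20% gave 67.16%, 30.77% and 6.09%.

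**Step 4: effect on stopping at 5 mg.** At flat 5%, 10% and 20%, the whole-trial chance of stopping there is 0.40%, 2.79% and 16.66% as written (added-three reading), against 0.09%, 1.09% and 10.61% under a rule of two or more in six. The differences, 0.31, 1.70 and 6.05 points, are the disputed path.

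**The case against.** On the label, the strongest reply is that the protocol uses its terms consistently: MTD is the level that stops escalation and TDL is the tolerated level below it. Objective 1.2.1 asks for both, the 1/6 criterion is attached only to the TDL, and no dosing decision changes. That stands, and it limits the harm to reporting; the 8% to 98% figures are the chance that the label is used, not the chance of a wrong dose. It does not remove the problem that a result named maximum tolerated is a rejected dose.

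On 5 mg, the reply is that a dedicated paragraph, placed after the general tables, is naturally read as overriding them. A stricter stop at the lowest level may also be deliberate, and the error is on the cautious side. A stricter stop would be legitimate if stated. But nothing says that the paragraph prevails, and Table 1 lists the 5 mg level and refers to Table 2 for its rules. Even if the paragraph prevails, on the added-three reading the order of events alone decides between stop and continue at the same 1/6.

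The disputed path is uncommon over the whole trial, and the higher figures rest on high assumed DLT rates. The DLT definition is fairly restrictive, since uncomplicated grade 4 cytopenia does not count, so those scenarios should not be taken as expected. Section 5 leaves dose decisions to the principal investigator, who still needs one rule fixed in advance.

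**Conclusion.** The point holds, and it should be corrected. The mislabelled MTD affects what is reported whenever escalation stops: 8%, 27% and 67% of trials at flat DLT rates of 5%, 10% and 20%, and 73% to 98% under the rising scenarios. It exposes no Phase 2 patient to the failed dose.

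The 5 mg contradiction concerns one outcome on the added-three reading and two on the all-six reading. On the added-three reading its chance over the whole trial is 0.3% to 11% across the assumed rates, and about 12% to 20% once 5 mg is opened at a 5 mg risk of 5% to 20%. It is rare, but it decides whether Phase 2 opens. The probabilities depend on the assumed rates; the contradiction does not. The 25 mg gap is minor.

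**What to change.** In Section 5, Table 2 and the TDL definition:

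- Call the level with two or more DLTs the non-tolerated (maximum administered) dose.
- Define MTD and TDL as the highest level with at most one DLT in six evaluable patients, including 25 mg if it clears, and have objective 1.2.1 report that level. The two terms then name one dose, which the text should say.
- At 5 mg, stop the study for two or more DLTs in total among up to six patients. If a stricter stop is intended, say so, base it on the total count, and exempt 5 mg from the Table 2 row for the Phase 2 dose and from the TDL definition.

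The cost is wording; no cohort or dose level is added. Choosing the looser 5 mg stop sends more trials on to Phase 2 at 5 mg, by 0.3, 1.7 and 6.1 percentage points at flat rates of 5%, 10% and 20%. Phase 1 size stays as the existing rules set it; the chance of exceeding 18 patients is below 0.5% in every scenario above.
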